4.4. Assessments

Study assessments will focus on the feasibility (e.g., recruitment, implementation of the intervention), treatment adherences, and safety measures. A list of assessments by the study visit is summarized in **Table 1**. Assessments are categorized as either general and medical assessments, safety assessments, substance use assessments, or methadone treatment and satisfaction assessments. A detailed description of each assessment is provided following the study assessment timetable.

Table 1: Study Assessment Timetable

Study visit number	Visit 1	Visit 2*_	Visit 3	Visit 4	Visit 5	Early termination	
Visit location**	OTP/remote	Pharmacy	OTP, Pharmacy, remote	OTP, Pharmacy, remote	OTP, Pharmacy, remote	OTP, Pharmacy, remote	
Assessment/Activity	Screening/ Baseline	Methadone dosing and dispensing	1 Month After Visit 2	2 Months After Visit 2	3 Months After Visit 2		As needed
General and Medical Assessments							
Recruitment Log	x						
Prisoner Status Assessment	x		x	x	x		x
Informed Consent/HIPAA/ Medical Release Form	x						x
Master Enrollment Log	x						
Inclusion/Exclusion Checklist +	x						
Locator Form	x		x	x	x		x
Demographics	x						
Medical History	x						
Substance use history	x						
Charlson Comorbidity Index	x						
Concomitant Medications	x		x	x	x		x
Study Completion					x	x	
Protocol Deviations							x
Missed Visit							x
Safety Assessments							
Patient Health Questionnaire (PHQ-9)	x		x	x	x	x	
P4 suicide screener (P4 screener) (Follow-up assessment will be triggered by the PHQ-9 result) ++	x		see ++	see ++	see ++		x
Safety Event Response Checklist	x		x	x	x		x
Pregnancy and birth control assessment	x		x	x	x		x
Substance Use Assessments							
Urine Drug Screen (UDS) (the OTP records)	x		x	x	x		x
Timeline Followback (TLFB)	x		x	x	x	x	
Methadone Treatment and Satisfaction Assessments							
Methadone Call Back (once)			see +++	see +++	see +++		x+++

Study visit number	Visit 1	Visit 2*_	Visit 3	Visit 4	Visit 5	Early termination	
Visit location**	OTP/remote	Pharmacy	OTP, Pharmacy, remote	OTP, Pharmacy, remote	OTP, Pharmacy, remote	OTP, Pharmacy, remote	
Assessment/Activity	Screening/Baseline	Methadone dosing and dispensing	1 Month After Visit 2	2 Months After Visit 2	3 Months After Visit 2		As needed
(the OTP records)+++							
OTP's Psychosocial Counseling Attendance Form (the OTP records)	x		x	x	x	x	
Methadone Visit Checklist++++		x	x	x	x		x
End of Methadone Medication Form					x	x	
Treatment Satisfaction Survey	x		x	x	x	x	

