Missed Study Assessment Visit: This form is designed to capture the reason a study visit was missed. Once the visit window closes without completion of the visit, this assessment will be completed directly in the electronic data capture system. Completing this form will remove the requirement for all assessments scheduled for that visit. Active tracking and follow-up should be performed for all missed visits.

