4.4.3. Substance Use Assessments

Urine Drug Screen (UDS): Urine drug screens will be performed once a month at the OTP as part of usual care for each participant during the study. The monthly urine specimens collected at the OTP are screened via enzyme immunoassay (EIA) and liquid chromatography-mass spectrometry (LCMS) is used for result confirmation to test for the following drugs: opiates, oxycodone, fentanyl, barbiturates, benzodiazepines, cocaine, amphetamine, methamphetamine, marijuana (THC), methadone, and ecstasy (MDMA). Monthly UDS data collected at the OTP will be documented into the UDS CRF at each monthly study visit via medical record review. Any UDS results demonstrating ongoing opioid use or other illicit/nonmedical substance use (e.g., cocaine) will be reported to the site PI to determine whether the participant should continue in the study.

Timeline Followback (TLFB): The Timeline Followback (TLFB) assessment will be used to collect self-reported information on substance and alcohol use over a 30-day look-back period, for which it has shown high test-retest reliability and validity (Sobell and Sobell 1992; Sobell and Sobell 2000). Participants will be asked to report daily substance and alcohol use since the previous TLFB assessment at the Intake/Baseline Visit and each monthly research visit. If a participant discontinues study participation early, the TLFB assessment also will be administered at the Early Termination Visit.

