The enrolled participants will receive their methadone under the supervision of study pharmacist during the study period. All other aspects of routine care will remain the same. Study participants will attend the pharmacy the same number of times/week as required at the OTP at the time of study enrollment for methadone administration and dispensing of take-home doses. Study participants will continue to receive their usual care at the OTP (e.g., counseling, prescription orders, urine drug screen), and they will return to their OTP at the end of the study. Study participants will also be able to, alternatively, withdraw from participating in the study at any point during the study period.

8. **Justification for inclusion of a placebo or non-treatment group.**

There is no placebo or non-treatment group in this study.

9. **Handling of missed visits and substance use**

Although the study participants will be stable patients, it is possible that they relapse to illicit drug use which may be manifested by missing appointments. It is also the possibility that scheduling conflicts may occur during the study, which will be addressed as described below.

- **If a participant presents to the pharmacy for take-home methadone administration/dispensing earlier or later than their scheduled visit date**, pharmacy staff will contact the prescribing physician (Site PI) before any medication is administered/dispensed to determine the course of action. Participants will be directed to the OTP for evaluation and medication administration/dispensing for that visit. Pharmacy staff will contact the OTP and the site PI to inform them of this development and document the event in the **Methadone Visit Checklist**. Possible outcomes of this evaluation may include:

- (1) return to pharmacy dispensing condition,
- (2) return to routine OTP methadone dispensing, or
- (3) loss of some or all of take-home methadone privileges for up to 6-months.

The outcome of the evaluation will be communicated the pharmacy and research staff as soon as possible.

- **If the participant fails the OTP program's routine methadone take-home recall procedure during the study or any tampering/diversion is suspected**, the participant will be discontinued from the study and returned to the OTP for methadone dosing and adjustment of their take home schedule as determined by the OTP provider.

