- **If illicit or non-prescribed opioid use is reported, found on drug testing, or suspected at any time during treatment**, the participant will be contacted to perform at least one random urine drug use test prior to the next scheduled visit and referred to the study physician for an assessment and to determine whether the participant should continue in the study.
- **Any non-prescribed use of benzodiazepines that is detected will prompt analogue measures to those adopted for opioid use**. The abuse of other substances or alcohol will result in early termination from the study and return to the OTP for methadone dosing and possible adjustment of the take home schedule.

Missing monthly research assessment visits and the rule for early study termination

- If the participant misses a scheduled monthly research assessment visit, alternative visits will be scheduled to collect the data.
- Missed visits will be documented using the Missed Visit Form. Remote/virtual interviews by phone or a Duke-approved teleconferencing platform for research may be used to collect study assessments for missed visits.

10. **Participant Discontinuation**

All participants will be followed for the duration of the study (approximately 3 months for pharmacy OUD maintenance) unless they withdraw consent, stop the methadone medication for OUD, die, or the investigator or sponsor decides to discontinue their enrollment for any reason. In addition to what is

described previously (discontinuation based on missed visits and/or illicit substance use), reasons for the investigator or sponsor to terminate a participant from the study may include, but are not limited to: study participation becoming unsafe, the participant becoming a threat to self or others, lack of funding, or early termination of the study for safety reasons. Of note, participants who discontinue methadone for any reason will be discontinued from the study.

- If a participant is discontinued from the study, an Early Termination Visit and End of Medication form should be completed as soon as possible following participant discontinuation to assess the participant's safety.

11. Description of what happens to participants receiving therapy when study ends or if a participant's participation in the study ends prematurely.

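### The missed-visit waiver makes no exception for urine drug screens and counseling attendance held in OTP records, so results on file may be left out of the positive-screen proportion

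*Combined protocol and SAP*

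**What the plan says.** The entry on missed study assessment visits in section 4.4.1 sets the rule in three steps. The form is triggered when the window has passed: "Once the visit window closes without completion of the visit, this assessment will be completed directly in the electronic data capture system". Its effect is then stated: "Completing this form will remove the requirement for all assessments scheduled for that visit". The entry ends with an instruction: "Active tracking and follow-up should be performed for all missed visits". Nothing in it separates items that the participant must answer from items read out of a record.

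Section 4.4.3 describes the drug screen as routine OTP care: "Urine drug screens will be performed once a month at the OTP as part of usual care for each participant during the study". Entry into the study data is tied to the research visit: "Monthly UDS data collected at the OTP will be documented into the UDS CRF at each monthly study visit via medical record review". Table 1 schedules the screen at Visits 3, 4 and 5 and gives its source in the row label, "Urine Drug Screen (UDS) (the OTP records)". Counseling attendance is scheduled at the same visits, and both Table 1 and section 4.4.1 take it from OTP records.

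Section 9 says of these stable patients that "it is possible that they relapse to illicit drug use which may be manifested by missing appointments". For research visits it adds: "If the participant misses a scheduled monthly research assessment visit, alternative visits will be scheduled to collect the data". It also allows phone or teleconference collection. Section 13.3 plans descriptive analyses, with GEE models considered for repeated outcomes, and gives no rule for missing data.

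**The concern.** A drug screen run as usual care does not depend on the research interview. The participant may skip a phone assessment and still give urine at the OTP that month. Followed as written, the waiver nevertheless removes the requirement to enter that result, because UDS is one of the assessments scheduled for the missed visit.

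If missed visits were unrelated to drug use, this would cost only some precision. The protocol itself suggests that they may be related. The results most at risk would then be those most likely to be positive, and objective d would be estimated mainly from participants who are doing well. Entry requires 12 months of negative tests, so few positives are expected, and one or two omitted results could change the reported picture.

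A second exposure concerns safety outcomes that rest on self-report: non-fatal overdose, ED visits and hospitalizations. If Visit 5 is missed and its checklist waived, no later scheduled visit would ask about the final month.

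**Working it through.** **Which items the waiver reaches.** The test is whether an item is scheduled for the monthly visit and whether it needs the participant.

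| Item | Source | Effect of a missed monthly visit |
|---|---|---|
| UDS | OTP record | Requirement removed, though a result may be on file |
| Counseling attendance | OTP record | Requirement removed, though the record may exist |
| TLFB, PHQ-9, satisfaction, birth control | Participant | Requirement removed; cannot be obtained without contact |
| Safety Event Response Checklist | Mainly self-report | Requirement removed |
| Methadone Visit Checklist | Pharmacist, at every pharmacy visit | Not dependent on the research visit |
| Call-back | OTP staff, random timing, own form | Not dependent on the research visit |

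The point therefore rests on the first two rows and, for Visit 5, on the safety checklist.

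**Size of the effect on objective d.** The plan states no figure to reproduce, and the sample is explicitly not powered. The only inputs from the documents are up to 20 participants (section 4.1) and three follow-up assessments (section 5), so 20 x 3 = 60 scheduled screens. All rates below are assumptions.

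Let m be the share of visits missed, p the positivity of screens on file for missed visits, and 5% the positivity at attended visits. If the omitted results are never entered, the study reports 5% on average. The true proportion is

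[60(1 - m) x 0.05 + 60m x p] / 60,

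so the understatement is m x (p - 0.05).

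| Visits missed (screens) | p = 5% | p = 25% | p = 50% | p = 100% |
|---|---|---|---|---|
| 5% (3) | 0 | 1.0 | 2.25 | 4.75 |
| 10% (6) | 0 | 2.0 | 4.5 | 9.5 |
| 20% (12) | 0 | 4.0 | 9.0 | 19.0 |

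Entries are percentage points. For example, m = 0.20 and p = 0.50 gives 0.20 x 0.45 = 9.0 points, a true 14.0% against a reported 5%.

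**The same in counts.** If all entered screens are negative and one positive screen is left out, the study reports 0/59 = 0% where the full record gives 1/60 = 1.7%. With two such screens it is 0/58 = 0% against 2/60 = 3.3%.

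**Bounds without a positivity assumption.** Suppose 3 positives are entered. With 3, 6 or 12 screens missing, the true proportion lies between 3/60 = 5.0% and (3 + 3)/60 = 10.0%, (3 + 6)/60 = 15.0% or (3 + 12)/60 = 25.0%. The available-case figures are 3/57 = 5.3%, 3/54 = 5.6% and 3/48 = 6.25%.

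**Safety events.** Section 4.3 has each follow-up cover the time since the previous assessment, so an event around a missed Visit 3 or 4 can be picked up at the next attended visit. After Visit 5 there is no next visit.

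**The case against.** The rule removes a requirement; it does not forbid entry. OTP results stay on file, Table 1 also marks UDS as needed, and a later record review could pick up an earlier month. A manual of operating procedures, not among the documents, may say more. This stands: the results may be left out, but the documents do not say that they will be.

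A reader might infer that sections 4.4.1 and 9 contradict each other. They can be read in sequence: alternative or remote visits come first, the form follows when the window closes, and tracking is still expected. What remains is a gap, because neither section says whether record-based items are still entered.

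The selection argument has limits. A relapsing participant may also miss the OTP screen, and then there is nothing to recover. Some will leave the study under the rules on substance use, or under the rule in section 15.2 on two consecutive missed visits. Both points reduce the likely size.

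Three stronger readings are tempting and are not supported:

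- That pharmacy and call-back data are cancelled too. The pharmacist's checklist is completed at every pharmacy visit, and call-backs are random events with their own form.
- That positive screens would not reach the site PI. That person is medical director of both OTP clinics, and the triggers in sections 9 and 15.2 do not depend on a research visit.
- That all safety events after Visit 4 are lost. Deaths and fatal overdoses are sought through records and locator contacts, and pharmacists record safety concerns at pharmacy visits.

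Finally, UDS is a secondary, descriptive outcome in a small pilot. That lowers the stakes, but does not make the reported proportion less open to bias.

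**Conclusion.** The concern holds for UDS and counseling attendance. As worded, the waiver covers data that need no participant contact, and the plan's own remark on relapse gives a reason to expect that the omitted screens may differ from those entered. Objective d could be understated.

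The size cannot be fixed from the documents. Under the assumed rates it runs from 0 to 19 percentage points. Zero is a real possibility: it applies if missed and attended visits have equal positivity, or if staff abstract the results regardless. Positivity below 5% at missed visits, which the assumed range leaves out, would reverse the direction.

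The safety exposure is narrower. It concerns self-reported non-fatal overdose, ED visits and hospitalizations after Visit 4, in participants who miss Visit 5 and are not reached by other means. The change is worth making because it removes an avoidable source of bias at almost no cost.

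**What to change.** 1. In section 4.4.1, limit the Missed Visit form's waiver to items that need the participant's answers: TLFB, PHQ-9 and P4, satisfaction, and the pregnancy and birth control assessment.
2. State that UDS and counseling attendance are abstracted from OTP records for every month in which the participant is in the study, whether or not the research visit took place. Reword section 4.4.3 so that UDS entry follows the calendar month and not the visit.
3. Keep the Safety Event Response Checklist required for Visit 5, by phone or from available records. Identify it as the 3-month visit, since parts of the text number the last visit as 4.
4. Align section 9 with these changes, so that the order of rescheduling, remote collection and form completion is explicit.

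The cost is a few sentences of protocol text, a change to the data-capture set-up, and a few minutes of record review per missed visit. Screens that were never taken would still be missing.

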4.4.2. Safety Assessments

Patient Health Questionnaire (PHQ-9): The PHQ-9 (Spitzer et al., 1999) is a validated, self-administered version of the PRIME-MD, contains the mood (PHQ-9) module as covered in the original PRIME-MD. It will be administered at Intake/Baseline and repeated at each follow-up visit and the Early Termination Visit if participant discontinues study participation early. Endorsements of suicidality on the PHQ-9 (i.e., if the participant answers Q9 ("Thoughts that you would be better off dead, or of hurting yourself in some way") as

“Several days”, “More than half the days” or “Nearly every day”) will trigger the completion of the P4 Screener form and an immediate report to the study’s physician and PI.

P4 Screener for suicide risk: The P4 Screener (Dube et al., 2010) is a brief measure (approximately 5 minutes) used for assessing potential suicide risk in primary care. The participant will answer 4 questions regarding past attempts, a plan, probability of completing suicide, and preventive factors at screening to exclude active suicidal ideation at Intake/Baseline. If the participant answers “Yes” to Question 2 of P4 Screener, “Have you thought about how you might actually hurt yourself?”, research staff will ask the participant additional clarifying questions to assess suicidality (Suicidal Risk form). A safety standard operating procedure will be indicated in the Manual of Operating Procedures (MOP), including the decision tree, assessment processes and documentation, and procedures to contact the study physician, study pharmacist, and the designated on-site crisis responder for assessment of the participant’s intent to harm and disposition.

Pregnancy and Birth Control Assessment: This form will document childbearing potential, and female participants' self-reported pregnancy status and use of an acceptable method of birth control. The Pregnancy and Birth Control Assessment will be collected during screening (Visit 1) to determine eligibility. For females of childbearing potential: Self-reported contraceptive use and pregnancy status will be performed at Visit 1 to confirm participant eligibility. Birth Control assessment and self-reported pregnancy question will also be administered at Visits 2 through 4. Pregnancy occurring during the study will be reported to Site PI for additional clinical monitoring, referral to pre-natal care (as needed), and the participant will be withdrawn from the study.

Safety Event Response Checklist: As methadone is an approved medication being prescribed in accordance with the approved usage, there would be no need to capture Adverse Events (AEs) per se, as the likely AEs are already known. However, in terms of compliance, informing dosing, side effects or monitoring those aspects, a solicited collection of information is relevant. To aid the collection of safety events, a tool in the form of a Safety Event Response Checklist with solicited symptom information, yes/no responses, and level of severity (mild, moderate, severe) will be developed for addition to the Manual of Operating Procedures (MOP). The checklist will be used by research staff to obtain self-reported information from each participant at each research visit. The MOP will specify the process of reporting safety events that may require interventions (such as side effects, reported loss of medication, call-back failure) to study physician (Site PI) and pharmacists, as well as to the Study PI.

For the purposes of this protocol, the following safety events will be collected and reported to assist with monitoring of methadone treatment and compliance. Side effects of the medication may include but are not limited to: headache, nausea, vomiting, constipation, excessive sleeping/insomnia, excessive sweating, pain, swelling, and overdoses.

In addition, we will collect all failure to respond to random call-back or to return the appropriate amount of medication, reported loss of medication, ED visits, hospitalizations, and death of any participant who provided written informed consent.

Following informed consent, the protocol-specified safety events will be solicited and recorded at each monthly research visit (including the Early Termination Visit if the participant discontinues study participation early), according to the outlined procedures. If a reportable safety event suggests medical or psychological deterioration or lack of responsible handling of methadone, it will be brought to the attention of the study clinician for further evaluation. The safety event will be medically managed, reported, and followed in accordance with applicable regulatory requirements. The participant may need to return to the OTP for extra visits or termination from the study with a return to the OTP for methadone administration and dispensing and changes in take-home levels in order to adequately manage an identified safety event.

Hospitalizations: Hospitalization for any medical and/or psychiatric reason will be reported accordingly on the Safety Event Response Checklist. All hospitalizations will be assessed by self-report at each monthly research visit or Early Termination Visit if participant discontinues study participation early.

Overdoses: Non-fatal overdoses since the last visit will be captured via self-report using the Safety Event Response Checklist at each monthly research visit following consent. Research staff will report overdose events to PI who will arrange with the site PI to terminate the participant from the study and return the participant to the OTP for medication administration, change in take home regimen, and other appropriate

intervention. Data on fatal overdoses may be collected via medical chart record review, if medical records data is available, or during participant tracking for follow-up interviews. Information from records will be supplemented with information from contacts with persons listed on the participant's locator form when participants are lost to follow-up throughout the study. Fatal overdoses will be captured on the Safety Event Response Checklist.

Death: All deaths, regardless of cause, will be captured for this study. These events will be identified through the participants' locator information, or when possible through using state medical examiner records, National Death Index, and/or review of medical records. Deaths will be reported using the Safety Event Response Checklist.

